6. SAFETY MONITORING AND REPORTING PLAN

The study will be conducted according to Good Clinical Practice (GCP) guidelines, the Declaration of Helsinki, US 21 Code of Federal Regulations (CFR) Part 50 – Protection of Human Subjects, and Part 56 – Institutional Review Boards. An independent Medical Safety Monitor (MSM), monitors from an Independent Contract Research Organization (CRO) and a Data Safety Monitoring Board (DSMB) will provide study oversight.

7. SUBJECT WITHDRAWAL

7.1 Description of Subject Completion

Subjects are considered to have completed the study if they completed three HB-adMSC fusions and the follow-up study visits at 6 and 12 months and the two year post-infusion telephone interview.

7.2 Withdrawal of Individual Subjects

The research team will make every reasonable effort to keep each subject in the study through the two year end of study telephone interview. If a subject withdraws from the study, the reason for withdrawal will be documented in the study records. Possible reasons for withdrawal include: adverse experiences, protocol non-compliance, lost to follow-up, at the discretion of investigator, the DSMB, the study sponsor, or other regulatory agencies. Study data and biological samples collected up to the point of withdrawal will remain in the study database for analysis.

7.3 Withdrawal of Subject from the Study Following Adverse Events

The PI will determine if an adverse event (AE) is of sufficient severity to require stopping subject participation. The subject (or LAR) may also voluntarily withdrawal from the study due to what he/she perceives as an intolerable AE. If the withdrawal from the study is due to an AE, the subject will be offered appropriate care under medical supervision until the symptoms of the AE resolve or the subject's condition becomes stable. Subsequent review by the MSM, DSMB, IRB or the study sponsor may also result in the suspension of further enrollment.

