Safety Monitoring and Follow-Up	Subjects will be monitored and assessed for infusion related toxicity for the first 4hr. after the infusion and by telephone 24hr. after each infusion. Safety assessments will be conducted at the study follow-up clinic visits 6 and 12 months, and 2 years (telephone call) after the last HB-adMSC infusion, or more frequently if infusion related adverse events are suspected.
Statistical Analyses	The data will be analyzed using general linear mixed models (GLMMs) to estimate differences across time points (pre- and post-treatment).
Stopping Rules	
The stopping rules listed below will trigger cessation of enrollment and potential study closure pending a comprehensive DSMB safety review.
 
 1. Any infusion related death. 2. An infusion related, sustained (over 3 minutes) episode of hypoxia (SaO₂ of less than 80%) or the new requirement for mechanical ventilation. 3. Grade 4-5 CNS cerebrovascular ischemia event or Grade 4-5 seizure event as defined in the NCI CTCAE v4.0 occurring within 48 to 72 hours of the infusion. 4. Any Grade 4-5 Adverse Event as defined in the NCI CTCAE v4.0 and determined to be temporally related to the HB-adMSC infusion by the Medical Safety Monitor and/or DSMB.

ABBREVIATIONS

adMSCs-Adipose Derived Mesenchymal Stem Cells
ADL-Activities of Daily Living
AE-Adverse Event
ANAM-Automated Neuropsychological Assessment Metrics
ARDS-Adult Respiratory Distress Syndrome
CAT-Calibrated Automated Thrombogram
CBC-Complete Blood Count
CCI-Controlled Cortical Impact
CD142-Tissue Factor or Platelet Tissue Factor
CFU-Colony Forming Unit
CGMP-Current Good Manufacturing Practices
CFR-Code of Federal Register
CMP-Complete Metabolic Panel
CNS-Central Nervous System
CRF-Case Report Form
CRO-Contract Research Organization
CRU-Clinical Research Unit
CSF-Cerebral Spinal Fluid
CTCAE-Common Terminology Criteria for Adverse Events
CXR-Chest X-Ray
DSMB-Data Safety Monitoring Board
DTI-Diffusion Tensor Imaging
DVT-Deep Vein Thrombosis
EMR-Electronic Medical Record
ESC-Embryonic Stem Cells
ETOH-Ethanol/Alcohol
F-Fibroblast
FA-Fractional Anisotropy
FDA-Food and Drug Administration
GCP-Good Clinical Practice
GCS-Glasgow Coma Scale
GLMM-Generalized Linear Mixed Model
GM-Gray Matter
GOAT-Galveston Orientation and Amnesia Test
GOS-E-Glasgow Outcome Scale - Extended
HB-adMSC's-Hope Biosciences' Autologous Adipose-Derived Mesenchymal Stem Cells
HIPAA-Health Insurance Protection and Portability Act

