3.6 Visits #3 thru 5: HB-adMSC Infusions

The infusion visits will be conducted in the CRU. Subjects will receive a total of 3 infusions (2×10^8 total cells per dose) administered over a 6 week period with 14 day intervals between infusions (+/- 3 days). The volume of each infusion will be 250mL infused over a 1hr. period (+/- 5 min.) at a rate of 4-5mL per minute.

At each infusion visit, the subject will undergo the following study procedures:

1. Interval H&P update (*detailed neuro exam if indicated from interview and physical exam, current medications and recent vaccinations*),
2. Confirmation the subject started prophylactic Lovenox injections and review of the Lovenox medication logs at follow-up visits,
3. A pregnancy test will be repeated for female subjects of child bearing potential (if applicable),
4. Vital signs (Heart Rate, BP, Resp., Temp., SpO₂),
5. Insertion of a peripheral IV line,
6. Blood sample for clinical labs (CBC with diff., CMP, coagulation and renal function panels),
7. Benadryl and Solumedrol will be given as pre-meds before the infusion. The dose for both drugs will be 25mg for subjects <100kg. or 50mg for subjects $\geq 100\text{kg}$.
8. A “time out” verification of patient/consent/procedure/cell product will be performed,

9. The HB-adMSC infusion will be given by through the peripheral IV,
10. The subject will then be monitored for a minimum of 4hr.

Vital signs will be continuously monitored during the infusion and recorded at 15 minute intervals. Vital signs will be recorded at the end of the infusion and then every 15 minutes x 4 (1st hour), and then every 30 minutes x 4 (next 2 hours), and then every hour until discharge from the CRU, or more frequently if clinically indicated. A chest x-ray may be obtained if clinically indicated to assess pulmonary AE/SAE's. The subject will be contacted by telephone 24hr. after each infusion visit to determine if adverse events have occurred. Each infusion visit is expected to take around 6 hours to complete.

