3.7 Visit #6: Six Months Post-Infusion

Safety and outcome assessments will be conducted in the CRU and at the HMRI 6 months from the last HB-adMSC infusion. The visit will include:

1. Interval H&P update,
2. Vital signs (Heart Rate, BP, Resp., Temp., SpO₂),
3. Blood sample for clinical labs (CBC with diff., CMP, coagulation and renal function panels) and neuro-inflammatory biomarkers,
4. A pregnancy test will be repeated for female subjects of child bearing potential (if applicable),
5. PET/DT-MRI,
6. Neurocognitive/functional outcome assessments.

The visit is expected to take about 8 hours and may require two days to complete the assessments and brain imaging.

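### Section 7.3 treats the PI's response to a severe adverse event as withdrawal from the study, and no supplied text lets a subject stop infusions and stay in follow-up

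*Protocol*

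**What the plan says.** Protocol section 3.6 sets the regimen: "Subjects will receive a total of 3 infusions", at 14-day intervals. An adverse event after the first or second infusion therefore raises the question of whether to give the next one.

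Section 7.3 covers adverse events that are severe enough to act on: "The PI will determine if an adverse event (AE) is of sufficient severity to require stopping subject participation". The section is headed as withdrawal from the study. It adds that the subject or LAR may also withdraw, and that after a withdrawal for an adverse event care is offered "until the symptoms of the AE resolve or the subject's condition becomes stable". That is clinical care, not the scheduled study assessments.

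Section 7.2 treats adverse events as a ground for leaving: "Possible reasons for withdrawal include: adverse experiences, protocol non-compliance, lost to follow-up". On data, it says: "Study data and biological samples collected up to the point of withdrawal will remain in the study database for analysis". It does not mention data after that point. It does require the reason for withdrawal to be recorded, and it promises reasonable effort to retain each subject to the two-year call. Section 7.1 counts a subject as a completer only after three infusions and all follow-up.

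Follow-up is timed from the final dose. Visit 6, for example, falls "6 months from the last HB-adMSC infusion" (section 3.7).

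**The concern.** Stopping treatment and leaving the study are different events. A subject can be taken off further infusions and still be seen at 6 and 12 months and telephoned at 2 years. If the protocol offers only withdrawal from the study, the subjects most likely to leave for an adverse event are those who tolerated the cells worst.

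Two sets of results are exposed. One is the later safety data at 6 months, 12 months and 2 years. The other is the set of 6-month changes in imaging, neurocognitive and functional outcomes, which would rest on subjects who tolerated treatment better. The core of the primary objective, acute infusional toxicity over the 4-hour observation and the 24-hour call, is collected around each infusion given and is much less affected.

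**Working it through.** **Step 1. Is the rule written elsewhere?** These are the other places where a stop of infusions alone could appear:

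- Synopsis, Stopping Rules: the "stopping rules listed below will trigger cessation of enrollment and potential study closure". These act on the trial, not on one subject's next dose.
- Synopsis, Safety Monitoring and Follow-Up: assessments at 6 and 12 months and 2 years, "or more frequently if infusion related adverse events are suspected". This helps only subjects who are still in the study.
- Section 3.6: the infusion-visit steps include an interval history and examination but no criterion for withholding a dose.
- Section 4 (Risks): classifies and monitors events, with no individual dosing rule.
- Tables 1a and 1b: assume three infusions.
- Section 7.1: has no category for a subject who stops dosing but completes follow-up.
- SAP: silent on partly dosed subjects.

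None supplies the rule. Section 6 beyond its introduction, Appendix 3 (the staggered infusion plan for the first four subjects) and sections 2, 9 and 10 were not supplied, so a rule could stand there.

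**Step 2. How many might leave?** N = 24 (section 8.1). The documents give no rate of withdrawal for adverse events, so p is assumed. With k ~ Binomial(24, p):

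| Assumed p | Expected k = 24p | P(k ≥ 1) = 1 − (1 − p)^24 | P(k ≥ 2) | P(k ≥ 4) |
|---|---|---|---|---|
| 2% | 0.48 | 38% | 8% | 0.1% |
| 5% | 1.2 | 71% | 34% | 3% |
| 10% | 2.4 | 92% | 71% | 21% |

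**Step 3. Bias in the 6-month mean change.** Assume that the true mean change over all 24 is zero, and that leavers would have changed d SD less than the rest, with d between 0.5 and 1.0 (assumed). If the rest have mean m, then k(m − d) + (24 − k)m = 0, so m = kd/24. Since E(k) = 24p, the expected bias is p × d:

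| Assumed p | d = 0.5 | d = 1.0 |
|---|---|---|
| 2% | 0.010 SD | 0.020 SD |
| 5% | 0.025 SD | 0.050 SD |
| 10% | 0.050 SD | 0.100 SD |

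The yardstick is the 95% CI half-width for a mean change, t(0.975, n − 1)/√n in SDs of change. With n = 24 it is 2.069/4.899 = 0.42, and with n = 20 it is 2.093/4.472 = 0.47. The expected bias is therefore between 0.010/0.42 = 2% and 0.100/0.42 = 24% of the half-width.

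Specific outcomes within that range of assumptions:

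- One leaver at d = 0.5: 1 × 0.5/24 = 0.02 SD, or 5% of the half-width of 0.43 at n = 23.
- Four leavers at d = 1.0: 4 × 1.0/24 = 0.17 SD, or 36% of the half-width of 0.47 at n = 20. By Step 2, four or more leavers has a chance of 0.1% to 21%.

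**Step 4. Does the planned mixed model remove this?** No, if leaving is unrelated to baseline. Keeping the leavers' baselines in a random-intercept model gave simulated mean estimates of 0.040 to 0.044 SD (two leavers, d = 0.5) and 0.166 to 0.169 SD (four leavers, d = 1.0), at pre-post correlations of 0.5, 0.8 and 0.9. The formula kd/24 gives 0.042 and 0.167. The simulation used known variances and no age term.

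**Step 5. Late safety, a constructed illustration.** Suppose three subjects leave and one of them has the only late event. The study then reports 0/21, with a two-sided 95% upper limit of 1 − 0.025^(1/21) = 16.1%. With everyone followed it would report 1/24 = 4.2%, with an exact upper limit of 21.1%.

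**The case against.** The best case against is that 7.3 governs withdrawal from the study, so its silence on stopping treatment alone is not a rule that ends follow-up. The supplied text leans towards retention: the effort promised in 7.2 has no exception for adverse events, and timing from the last infusion works after one, two or three doses. This stands. A reader might infer that the protocol orders subjects out of follow-up when dosing stops. The documents do not support that, because nothing forbids keeping them.

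A reader might also infer that withdrawal is the only response to any adverse event. It is not. Section 7.3 sets a severity threshold; below it subjects stay in, and the plan provides for extra safety assessments, a chest x-ray if indicated, and an examination before each infusion.

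Nor would a single-arm design hide the selection. Section 7.2 has the reasons documented and the earlier data kept, so with 24 subjects it is visible who left and why. What is lost is their later outcomes, which would be unobserved in any design.

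The size is also open to challenge. The rates and the deficit d are assumptions, and the largest figures need an unlikely combination. The option to stop infusions alone matters only between the first and third infusion, about four weeks, and the assumed rates are not limited to that window. Some subjects will withdraw themselves whatever 7.3 says, so the bias shown is an upper bound on what a change could recover.

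What survives is narrower. The one supplied section on the PI's decision after a severe adverse event leads to withdrawal and clinical care, and no supplied text says that a subject taken off infusions stays in scheduled follow-up.

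**Conclusion.** The point holds as a gap in wording with a real but modest consequence. Where 7.3 is applied, after any of the three infusions, later safety data and 6-month outcomes would be missing for the subjects who tolerated the cells worst. Under the assumed rates and deficits the expected bias is about 0.01 to 0.10 SD, well inside the CI half-width, and the effect is small if few withdraw. The case for acting rests more on the late safety record of a safety study than on the efficacy estimates.

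The conclusion depends on the supplied text. A rule on holding infusions in the rest of section 6 or in Appendix 3 would answer it. The change is worth making because it is cheap, but the trial's core primary assessment does not depend on it.

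**What to change.** In section 7.3, separate two decisions: the PI may stop further infusions for an adverse event without ending participation, and the subject or LAR may withdraw consent for follow-up. State that any subject who received at least one infusion stays in the 24-hour call, Visits 6 and 7 and the 2-year call, timed from the last infusion received, and in the safety and outcome data. The exceptions are withdrawal of consent for follow-up and any assessment that is medically unsafe for that subject.

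The cost is protocol and consent wording, plus completing visits that are already scheduled for every subject, including the PET/DT-MRI at Visit 6. The change cannot retain subjects who withdraw consent themselves. For anyone already withdrawn, report the number, timing and reason from the withdrawal records.

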8. STATISTICAL ANALYSIS PLAN

8.1 Sample Size and Power

A total of 24 patients will be enrolled in the study. We do not provide a power analysis for any outcomes since no formal hypothesis testing will be conducted. Instead, we will calculate estimates of treatment effect and 95% confidence intervals for all measures. We will also calculate probabilities of treatment benefit using Bayesian analyses and conservative neutral priors. Given that this is a Phase 1/2a study, there are no prior studies from which we could derive informative priors. Therefore our approach will be to use neutral priors meaning that a priori they will be centered at a null treatment effect. However, we will restrict the prior range (ie, 95% prior credible interval) to exclude large treatment effects that are almost never observed in human clinical studies.

8.2 Statistical Analyses

Volumetric, DT-MRI, neuropsychological, and functional outcome measures will be analyzed using general linear mixed models (GLMMs) to estimate differences across time points (pre- and post-treatment). We will examine all variables to determine that they are relatively symmetric and unimodal and examine residuals from each model to ensure reasonable adherence to model assumptions. The models will include time of assessment (pre- or post-treatment), and age (at study entry) as covariates and a random effect for subject to account for within subject correlation. Dependent variables will be the volume of whole brain gray matter, white matter, and CSF. Each dependent variable will be evaluated separately. Estimated differences at 6 months post treatment compared to pre-treatment will be reported along with 95% confidence intervals for all outcomes. We will also calculate probabilities of treatment benefit or clinically important effects.

8.2.1 Volumetric Analysis and Neurocognitive Outcomes

For volumetric analyses and neurocognitive outcomes, we will use the global test procedure recommended by Bagiella et al (Bagiella, 2010). This procedure allows analysis of multiple outcome measures in the assessment of intervention effects while controlling Type I error and maximizing power. To examine brain-behavior relations, we will first examine the distribution of variables to determine whether assumptions are met for Pearson or Spearman correlation approaches. To evaluate strength of brain-behavior relations, outcome scores will be correlated with specific macrostructural and microstructural metrics from the DTI. For global outcome, the GOS-EC score will be correlated with gray and white matter volumes and corpus callosum FA. For neurocognitive outcomes, the accompanying table shows the expected relations between outcomes and gray and white matter microstructural metrics. We expect positive correlation of dependent variables with FA and white and gray matter volume and negative correlation of dependent variables with MD.

Table 4:

Expected Relations of Neurocognitive Outcomes with Gray and White Matter Microstructure from Diffusion Tensor Imaging		
Neuropsychological Outcome	Microstructure: Gray Matter MD	Microstructure: White Matter FA
Processing Speed WAIS-IV Coding		Corpus callosum
Fine Motor 9-hole Pegboard Dexterity Test		Corticospinal
Verbal D-KEFS Verbal Fluency NIH Picture Vocabulary Test		Arcuate/superior longitudinal fasciculus
Working Memory NIH List Sorting Working Memory Test	Dorsolateral prefrontal cortex	
Declarative Memory Rey Auditory Verbal Learning Test	Lateral temporal cortex, hippocampus	
Attention NIH Flanker Inhibitory Control and Attention Test	Dorsolateral & ventrolateral prefrontal cortex	

8.2.2 Cytokine and Pro/Anti-Inflammatory Marker Analysis

For inflammatory cytokines, time course data will be analyzed using a GLMM to test differences across time between pre- and post-treatment. The dependent variables will be the neuroinflammatory biomarkers with time (to model the trajectory) and GOSE (3-4 or 5-8) as covariates and a random subject effect (to account for within subject correlation). Point estimates of pre- and post-treatment differences will be reported along with 95% confidence interval

8.2.3 PET Imaging Analysis

PET imaging analysis: Following completion of PET scanning, two main types of PET analyses will be completed:

8.2.3.1 Volume of Interest Analysis:

A hypothesis-driven VOI analysis where selected brain regions are examined will be conducted. Advantage of narrow search within regions involved in regulating the pain experience (e.g., anterior cingulate, insular cortex, nucleus accumbens, thalamus, amygdala, periaqueductal gray). Predefined VOIs obtained from data of previous studies are applied to image data and transferred to [¹¹C]ER-176 maps.

8.2.3.2 Statistical Parametric Mapping:

In these types of analyses, statistical parametric maps are obtained using whole brain image subtraction routines. Differences between volunteer groups (and covariates with phenotypic data) will be compared using the general linear model on a voxel by voxel basis within SPM8 and Matlab software with correction for multiple comparisons. Resulting Z-maps of statistical significance are mapped onto stereotactic space using volunteers' anatomically standardized T1-weighted MRIs. Only gray matter pixels and regions with specific binding will be included in the statistical parametric analyses (voxels with BPND values > 0.2). To compensate for small residual anatomic variation between subjects and to improve signal to noise ratio, a 3D Gaussian filter (FWHM 6 mm) will be applied to each scan. For

each subtraction analysis, one- or two-sample t-statistic values will be calculated for each voxel using a pooled smoothed variance across voxels. Areas of significant differences will be detected with a statistical threshold set to control for a Type-I error rate at $p = 0.05$ for multiple comparisons, estimated using the Euler characteristic based on the number of voxels in the grey matter and image smoothness. This threshold typically corresponds to $z=4.3$ to 4.6 , lower for large size regions after cluster volume correction is applied. Plans for implementing corrections based on false discovery rate (FDR) are underway. The standard Euler characteristic method controls for Family-wise Type-I error, the chance of any false positives. FDR is the proportion of false positives among suprathreshold voxels. The FDR is a more lenient measure of false positives than Family-wise Error and hence more powerful, while offering a principled way to control false positives. After significant statistical effects are obtained in SPM, regional data is extracted into SPSS, plotted to assess for outliers, and used in additional analyses (i.e. correlations with dependent variables). Data is tested for normality (uniformly encountered) and if not obtained, equivalent non-parametric analyses will be used.

## “A Clinical Trial to Determine the Safety and Efficacy of Hope Biosciences Autologous Mesenchymal Stem Cell Therapy for the Treatment of Traumatic Brain Injury and Hypoxic-Ischemic Encephalopathy”

### **8. STATISTICAL ANALYSIS PLAN**

#### **8.1 Sample Size and Power**

A total of 24 patients will be enrolled in the study. We do not provide a power analysis for any outcomes since no formal hypothesis testing will be conducted. Instead, we will calculate estimates of treatment effect and 95% confidence intervals for all measures. We will also calculate probabilities of treatment benefit using Bayesian analyses and conservative neutral priors. Given that this is a Phase 1/2a study, there are no prior studies from which we could derive informative priors. Therefore our approach will be to use neutral priors meaning that a priori they will be centered at a null treatment effect. However, we will restrict the prior range (ie, 95% prior credible interval) to exclude large treatment effects that are almost never observed in human clinical studies.

